5.1.3.2.5 Progression-free Survival

Since disease progression is assessed periodically, PD can occur any time in the time interval between the last assessment where PD was not documented and the assessment when PD is documented.

Hence, progression-free survival (PFS) is defined as the time (months) from date of randomization until date of documented disease progression or death due to any cause, whichever comes first. More specifically, PFS will be determined using all the assessment data up until the last evaluable visit prior to or on the date of (i) disease progression as defined by RECIST Version 1.1; or (ii) withdrawal of consent; or (iii) receiving subsequent anti-cancer therapy, whichever is earlier.

PFS will be calculated using derived responses and progression by RECIST Version 1.1 (whichever comes first) will be considered.

Death, regardless of cause, is always considered as a PD event. The detailed censoring rules for the analysis are summarized in [Table 9](#).

Table 9 Assignment of Progression or Censoring Based on Radiological Assessment

Situation	Date of Progression or Censoring	Outcome
No progression - treatment not started	Date of randomization	Censored
No progression	Date of last adequate radiological disease assessment	Censored
Treatment discontinuation for reasons other than disease progression	Date of last adequate radiological disease assessment with no documented progression	Censored
New anticancer treatment started prior to documented disease progression	Date of last adequate radiologic assessment no later than the initiation of new anticancer treatment	Censored

Situation	Date of Progression or Censoring	Outcome
Disease progression per RECIST Version 1.1	Date of the first reported progression	Progressed
Death without a PD	Date of death	Progressed

Note: An adequate radiologic assessment is defined as an assessment where the Investigator determined radiological response is CR, PR, SD, or PD. If PD and new anti-cancer therapy occur on the same day, will assume that the progression was documented first, e.g. outcome is progression and the date is the date of the assessment of progression.

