- c. Best response will be SD if the first time point overall response if after 35 days on study. Otherwise, the best response will be NE.
- d. Best response will be SD provided the criteria for PD have not been met from the first to second assessment.

* A best overall response of SD can only be made after the subject is on study for a minimum of 35 days (counted from Cycle 1 Day 1). If the subject is on study for less than 35 days, any tumor assessment indicating stable disease before this time period will have a best response of NE unless PD is identified.

^Subsequent documentation of a CR may provide confirmation of a previously identified CR even with an intervening NE (e.g., CR NE CR). Subsequent documentation of a PR may provide confirmation of a previously identified PR even with an intervening NE or SD (e.g., PR NE PR or PR SD PR). However, only one (1) intervening NE or SD will be allowed between PRs for confirmation. Note: in the following scenario, PR SD NE PR, the second PR is not a confirmation of the first PR.

Objective response rate (ORR) will be calculated using two methods:

Method #1: ORR will be calculated using a strict interpretation of RECIST Version 1.1.

Objective response will be derived as no/yes (0/1) variable. Patients with a BOR of confirmed CR or PR will be assigned ‘Yes’. Patients not having a BOR of confirmed CR or PR will be assigned ‘No’. Hence, ORR is defined as the proportion of patients with objective response being “Yes”.

Method #2: ORR_{UNCONFIRMED} will be calculated using all responses regardless of confirmation. Objective response will be derived as no/yes (0/1) variable. Patients with a BOR of confirmed CR, confirmed PR, unconfirmed CR or unconfirmed PR will be assigned “Yes”. All patients with other BOR values will be assigned “No”. Hence, ORR_{UNCONFIRMED} is defined as the proportion of patients with objective response being “Yes”.

Duration of Response (DOR) is the time between first response by RECIST Version 1.1 of CR or PR and the first date that progressive disease is documented by RECIST Version 1.1, or death. Patients who do not experience PD or death will be censored at the last tumor assessment date. Only those patients with confirmed responses will be included in this analysis. Censoring will follow the rules outlined below for PFS in [Section 5.1.3.2.5](#).

Clinical benefit rate (CBR) is defined as the proportion of patients with a BOR of confirmed CR, confirmed PR, or SD.

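### SAP Table 9 has overlapping rows with no stated precedence: a patient who stops treatment for a non-progression reason and later progresses can be read as censored or as an event, in PFS and in DOR

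*SAP*

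**What the plan says.** SAP section 5.1.3.2.5 defines PFS as time from randomization to documented progression or death. It then says "PFS will be determined using all the assessment data up until the last evaluable visit prior to or on the date of" RECIST progression, consent withdrawal or subsequent anticancer therapy, whichever is earliest. Stopping treatment is not in that list.

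Table 9 follows. Three of its rows matter here:

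- "Treatment discontinuation for reasons other than disease progression": Censored, at the "Date of last adequate radiological disease assessment with no documented progression".
- "New anticancer treatment started prior to documented disease progression": Censored, at the last adequate scan no later than the start of the new treatment.
- Progression per RECIST 1.1: an event, at the "Date of the first reported progression", with no condition attached.

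The note under the table adds: "An adequate radiologic assessment is defined as an assessment where the Investigator determined radiological response is CR, PR, SD, or PD". Its only tie-break concerns progression and new therapy on the same day.

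For DOR, SAP section 5.1.3.2.4 says "Patients who do not experience PD or death will be censored at the last tumor assessment date", and then "Censoring will follow the rules outlined below for PFS in" section 5.1.3.2.5.

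Protocol sections 12.3 and 10.7 keep scanning patients who stop for a reason other than progression, about every 2 months, until progression or study completion. Protocol section 13.5.4 leaves to the SAP the censoring of patients who have neither progression nor death.

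**The concern.** The new-therapy row states in its situation cell that the trigger must precede documented progression. The discontinuation row has no such condition in that cell. The protocol scans patients after a non-progression stop in order to find their progression, and one reading of this row would discard what those scans find.

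Two programmers could follow the same SAP and produce different PFS event sets. At stake are the PFS event count, the Kaplan-Meier PFS rates at 3, 6, 9 and 12 months and the Cox hazard ratio (SAP sections 6.2.7.1.3 and 6.2.7.2.3), and the Kaplan-Meier summary of DOR. DOR has no Cox model.

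**Working it through.** **1. Text check.** Take a patient who stops all study drug for toxicity at month 3 with stable disease, starts no new therapy, and has RECIST progression on a scan at month 7.

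| Rule | Result for this patient |
|---|---|
| Table 9, discontinuation row | Fits; censored |
| Table 9, RECIST progression row | Fits; event at month 7 |
| PFS definition and data window, SAP 5.1.3.2.5 | Event; a treatment stop is not a cut-off |
| PFS definition, protocol 13.5.4 | Event |
| Delegation of censoring, protocol 13.5.4 | Patient had progression, so not in the group left to the SAP for censoring |
| DOR sentence, SAP 5.1.3.2.4 (if a responder) | Event, but Table 9 is then imported |

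A patient treated beyond RECIST progression who then stops for toxicity also fits both rows, although protocol section 11.1.4 dates progression at the initial event.

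**2. The date cell.** Its closing words about no documented progression have two readings. They may limit the row to patients who never progress, which makes it a duplicate of the no-progression row. Or they may pick the last clean scan before a progression scan; the note allows an adequate scan to show progression, so that reading also makes sense. The wording does not decide.

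**3. Size.** No figure in the plan depends on this row, so there is nothing to reproduce. The documents give no non-progression stop rate and no share of stoppers who start new therapy. What follows is illustration only.

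*Simple count.* SAP section 6.2.13 uses 80% of patients progressed as a milestone: 0.80 × 106 = 84.8, so 85. If a share d of those progressions falls in patients who stopped for another reason, the censoring reading keeps 85 × (1 − d):

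- d = 5%: 81
- d = 10%: 77 (76.5)
- d = 20%: 68
- d = 30%: 60 (59.5)

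*Simulation.* Assumed: exponential PFS with median 5 months; 24 months of follow-up; 106 patients; no drug effect on PFS; 10% of first events are deaths and always count; scans every 6 weeks to about 9 months, then every 9 weeks, and every 60 days after a stop; stops uniform over 0.5 to 4 months; 25% of stoppers start new therapy 1 to 3 months later and are censored under both readings. Equal stops in both arms:

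| Stops | Events per 106, counted → censored | 12-month PFS, counted → censored |
|---|---|---|
| 5% | 100 → 97 | 23.2% → 24.3% |
| 10% | 99 → 92 | 22.9% → 25.2% |
| 20% | 97 → 83 | 22.6% → 27.7% |
| 30% | 95 → 74 | 22.2% → 30.5% |

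The 12-month level depends on where scans fall. Another run at 20% stops gave 19.6% → 23.8%, a similar upward shift.

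The assumed share starting new therapy matters. At 20% stops and 0 / 25 / 50 / 75% new therapy, about 18 / 14 / 10 / 6.5 progressions per 106 are discarded. If the censoring date is instead the last scan before the stop, 12-month PFS at 20% stops moves only from 22.6% to 23.0%.

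*Hazard ratio (trilaciclib to placebo).* Equal stops give no systematic shift. Unequal stops, counted → censored:

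| Stops, placebo / trilaciclib | Same hazard after stop | Doubled hazard after stop |
|---|---|---|
| 30% / 15% | 1.00 → 1.11 | 0.93 → 1.03 |
| 15% / 30% | 1.00 → 0.90 | 1.07 → 0.97 |

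Against a standard error of 2/√85 = 0.217 for the log hazard ratio, ln(1.11) = 0.104 is 0.48 of a standard error. With the date at the last scan before the stop, the 30% / 15% case is 1.00 → 1.00 at the same hazard.

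*DOR.* With the 4-month median in protocol section 4.1, the Kaplan-Meier median goes 4.3 → 4.3 months at 10% stops, 4.3 → 4.9 at 20% and 4.5 → 5.4 at 30%. With a doubled hazard after the stop it hardly moves (4.2 → 4.3).

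**The case against.** The best answer is that the qualifier is present, only in another cell. Each of the four censoring rows mentions the absence of progression once, and the discontinuation row does so in its date cell. The progression row is just as literal, and the surrounding text points to counting the event. SAP section 6.1.1 requires independent program validation with checks for consistency with the plan. Where the SAP differs from the protocol, protocol section 13 lets the SAP prevail, and the SAP's list of changes from the protocol is redacted, so a departure from the protocol is not in itself an error.

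Much of this stands. Censoring is not the only literal outcome, and the benign reading is the likelier intention. What remains is a conflict inside the SAP: two rows give opposite outcomes for the same patient, no precedence is stated, and DOR takes over the table. Validation cannot settle which row was meant.

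A reader might go further in two ways that the documents do not support. One is that the plan definitely discards progressions; the progression row and the PFS text say otherwise. The other is that the final PFS analysis might never be reached; SAP section 6.2.13 counts patients who have experienced a progression, not uncensored Table 9 events.

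**Conclusion.** The point holds as an unresolved overlap in Table 9, not as a settled rule to censor. If later progression is counted, nothing changes. If the row is programmed as censoring, documented progressions leave PFS and DOR, the event count falls and the Kaplan-Meier PFS estimates tend to rise even when stops are equal between arms. The hazard ratio can move in either direction when they are not.

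The size cannot be derived from the documents. The figures above rest on assumed stop rates, new-therapy share, PFS median and censoring date, and the largest systematic hazard-ratio shift in the tables is about half a standard error. PFS and DOR are supportive and outside the multiplicity procedure (SAP section 6.2.7.1.4), and lack of harm is assigned to OS (SAP section 5.1.2.4), so the myelosuppression conclusions are unaffected. It should be corrected before unblinding because the event set should not depend on how a programmer reads one row.

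**What to change.** Delete the discontinuation row, since the no-progression row already covers patients who stop and never progress. Alternatively, limit its situation cell to patients with no documented progression or death.

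In either case add one sentence: stopping one or more study drugs does not by itself censor a patient, and progression documented later, before any new anticancer therapy, is an event. Leave the handling of death to the existing text of the section, so that the new sentence does not qualify it. State that DOR follows the same rule. If censoring at discontinuation is wanted, make it a labelled sensitivity analysis that names its censoring date.

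The cost is one table row or one sentence in the SAP, with no new data. If the row was meant as a duplicate, no result changes.

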5.1.3.3. Occurrence of Grade 3 and 4 Hematologic Toxicities

Hematologic toxicities events are defined as any cycle where any hematologic lab value occurs that meets the CTCAE toxicity grade criteria for \geq Grade 3 and the value is treatment emergent. For details on which parameters are included and the definition of treatment emergent see [Section 5.2.4](#).

For the induction treatment period, the total number of hematologic toxicity events is the number of induction cycles in which there is at least one hematologic toxicity event. If a patient did not have any hematologic toxicity events, the value of 0 will be assigned to that patient. The number of induction cycles without hematologic toxicity events is calculated as total number of induction cycles received – total number of induction cycles with a hematologic toxicity event.

Therefore, any occurrence of a hematologic toxicity event during an induction cycle or the induction treatment period is defined as a binary variable (Yes or No); Yes if total number of induction cycles with a hematologic toxicity event ≥ 1 is observed, No for other scenarios.

5.1.3.4. ANC Nadir by Cycle

See table in [Section 5](#) for the definition of cycle nadir.

5.1.3.5. ANC, Platelet Count, Absolute Lymphocyte Counts (ALC), and Hemoglobin Change over Time

For the hematologic parameters consisting of ANC, hemoglobin, platelet count, and ALC, the observed lab values in each windowed visit as detailed in [Section 6.1.3](#) will be appropriately identified for further analysis.

5.1.3.6. Occurrence of Erythropoiesis Stimulating Agent (ESA) Administrations

Administration of ESAs is collected throughout the induction treatment period. Those induction cycles where ESAs are administered concurrently will be identified by comparing the start and stop dates of each ESA to the start of cycle and end of cycle. If any of the dates of administration of an ESA overlap with any dates between the start of cycle and end of cycle, that cycle will be considered as having an ESA administered. Data handling conventions for missing start and stop dates are described in [Section 6.2.5](#).

For the induction treatment period, the total number of ESA administrations is the total number of induction cycles in which there is at least one ESA dose administered; If a patient did not receive an ESA, the value of 0 will be assigned to that patient. The number of induction cycles

where ESAs were NOT given is calculated as total number of induction cycles received – total number of induction cycles where ESAs were administered.

Therefore, any occurrence of an ESA administration during the induction treatment period is defined as a binary variable (Yes or No); Yes if total number of induction cycles with ESA administration ≥ 1 is observed, No for other scenarios.

5.1.3.7. Occurrence of IV Antibiotic Uses

IV antibiotic administration is collected with concomitant medications which are coded using World Health Organization Drug Dictionary (WHO-DD) Version Sep2017. The criteria for identifying an IV antibiotic administration event is

- If the Therapeutic subgroup from WHO-DD Version Sep2017 (i.e. TEXT2 for CODE2) takes value “ANTIBACTERIALS FOR SYSTEMIC USE”, and
- The route of medication is “intravenous” or the route is “other” with the detailed specification as “IVPB”.

Each IV antibiotic with a unique start date during the induction treatment period will be defined as a separate event. Data handling conventions for missing start and stop dates are described in [Section 6.2.5](#).

Occurrence of an IV antibiotics administration during the induction treatment period is defined as a binary variable (Yes or No); Yes if total number of IV antibiotics administration ≥ 1 is observed, No for other scenarios.

5.1.3.8. Occurrence of Infection Serious Adverse Events (SAEs) and Pulmonary Infection SAEs

Each infection SAE is captured in the electronic database. The event terms are coded using the MedDRA Version 20.1. The criterion for identifying the proper infection SAE records is as follows: if the system organ class (SOC) from MedDRA takes value “INFECTIONS AND INFESTATIONS”, and the AE is a serious event.

Each infection SAE with a unique start date during the induction treatment period will be defined as separate event. Data handling conventions for missing start and stop dates for AEs are described in [Section 5.2.2](#).

Any occurrence of an infection SAE during the induction treatment period is defined as a binary variable (Yes or No); Yes if total number of infection SAE events ≥ 1 is observed, No for other scenarios.

5.1.3.9. Occurrence of Pulmonary Infection SAEs

Each infection SAE is captured in the electronic database. The event terms are coded using the MedDRA Version 20.1. The criterion for identifying the proper pulmonary infection SAE records is as follows: if the SOC from MedDRA takes value “INFECTIONS AND INFESTATIONS”, the PT takes values from [Table 10](#), and the AE is a serious event.

Table 10 PT List for Grouping Pulmonary Infection AEs

Category	Preferred terms
Pulmonary Infection AEs	Bronchiolitis
	Bronchitis
	Influenza
	Pneumonia
	Pneumonia bacterial
	Respiratory tract infection
	Upper respiratory tract infection
	Viral upper respiratory tract infection

Each pulmonary infection SAE with a unique start date during the induction treatment period will be defined as separate event. Data handling conventions for missing start and stop dates for AEs are described in [Section 5.2.2](#).

Any occurrence of a pulmonary infection SAE during the induction treatment period is defined as a binary variable (Yes or No); Yes if total number of pulmonary infection SAE events ≥ 1 is observed, No for other scenarios.

5.1.3.10. Occurrence Febrile Neutropenia

Each febrile neutropenia event is captured in AE data of electronic database, and “FEBRILE NEUTROPENIA” is a PT which can be used to identify the proper AE records. The event terms are coded using the MedDRA Version 20.1.

Each febrile neutropenia event with a unique start date during the induction treatment period will be defined as a separate event. Data handling conventions for missing start and stop dates for AEs are described in [Section 5.2.2](#).

Any occurrence of a febrile neutropenia event during the induction treatment period is defined as a binary variable (Yes or No); Yes if total number of febrile neutropenia events ≥ 1 is observed, No for other scenarios.

[REDACTED]

[REDACTED]

[REDACTED]

[REDACTED]

[REDACTED]

[REDACTED]

[REDACTED]

[REDACTED]

[REDACTED]

[REDACTED]

[REDACTED]

[REDACTED]

[REDACTED]

[figure not shown]
[REDACTED]

[REDACTED]

[REDACTED]

[REDACTED]

[REDACTED]

5.2. Safety Endpoints

5.2.1. Chemotherapy Exposure Endpoints

5.2.1.1. Duration of Exposure

Duration of exposure will be calculated for the overall treatment period as well as separately for the induction treatment period and the maintenance treatment period. Note that Duration of exposure will be different than Duration of the treatment period defined elsewhere, and it will only apply to exposure summaries.

Induction period duration of exposure (days) = Day 1 of last induction cycle – Cycle 1 Day 1 of induction phase + 21.

Maintenance period duration of exposure (days) = Day 1 of the last maintenance cycle – Cycle 1 Day 1 of maintenance phase + 21.

Overall period duration of exposure (days) = Day 1 of the last cycle (either maintenance or induction) – Cycle 1 Day 1 of induction phase + 21.

5.2.1.2. Number of Cycles Received

Patients are considered to have started a cycle if they have received at least one dose of any study drug (carboplatin, etoposide, atezolizumab or trilaciclib). In addition to the numeric summary for the number of cycles, the number of cycles for the induction treatment period will be categorized as 1, 2, 3 or 4. The number of cycles in the maintenance period will be categorized as: 1, 2, 3, 4, 5, 6, and > 6.

